**Table 5      Intervals Between Study Visits**

Interval	Optimal length of interval	Allowed interval 
Visit 1 → Visit 2	60 days	29 days - 81 days
Visit 2 → Visit 3	60 days	29 days - 81 days
Visit 3 → Visit 4	30 days	21 days - 60 days
Visit 3 → Visit 5	180 days	173 days - 271 days
Visit 5 → Visit 6	30 days	21 days - 60 days
Visit 5 → Visit 7 (Study termination) 	180 days	173 days - 201 days
Visit 5 → Visit 7 (Study termination)	360 days	353 days - 381 days

The investigator should arrange study visits within this interval as subjects may not be eligible for inclusion in the PPS cohorts if they make the study visit outside this interval. All visits and windows should be planned to use the day of last vaccination as the reference point.

The allowed intervals have been modified in keeping with ACIP guidelines to facilitate the safe scheduling of study visits during the COVID-19 pandemic situation.

 For subjects who have not yet reached the 6-month safety follow-up after the last dose at the time protocol amendment 7 took effect, Visit 7 will occur on Day 481.

#### 4.1.6.      Other Analysis Sets

Not applicable.

#### 4.1.7.      Subgroups

The following descriptive analyses will be performed by gender, race, ethnic origin and age group (6-8 weeks or  $\geq$ 8 weeks) for the following parameters:

- GMCs for PCV at one month after the 3rd and 4th vaccination in Group MenB+PCV and Group Placebo+PCV.
- Percentages of subjects with hSBA titers  $\geq$ LLOQ; for each of the 4 rMenB+OMV NZ test strains and for all strains combined at each timepoint that a blood sample result will be available in Group MenB+PCV and Group Placebo+PCV.

- Percentages of subjects with hSBA titers  $\geq 8$  (for strains M14459, NZ98/254, M13520) and  $\geq 16$  (for strain 96217); for each of the 4 rMenB+OMV NZ test strains and for all strains combined at one month after the 4th vaccination in Group MenB+PCV and Group Placebo+PCV

Analyses will be performed on the FAS.

## 4.2. Criteria for eliminating data from Analysis Sets

Elimination codes are used to identify subjects to be eliminated from analysis. Details are provided below for each set.

### 4.2.1. Elimination from Exposed Set (ES)

Code 1030 (Study vaccine not administered at all), code 900 (invalid informed consent), and code 800 (fraudulent data) will be used for identifying subjects eliminated from ES.

### 4.2.2. Elimination from Solicited Safety Set

A subject will be excluded from the Solicited Safety Set analysis under the following conditions:

Code	Condition under which the code is used
2160	Subject did not provide any post-vaccination solicited safety data

### 4.2.3. Elimination from Unsolicited Safety Set

A subject will be excluded from the Unsolicited Safety Set analysis under the following conditions:

Code	Condition under which the code is used
2150	Subject did not provide any post-vaccination unsolicited safety data

### 4.2.4. Elimination from Per-protocol analysis Set (PPS)

#### 4.2.4.1. Excluded subjects

A subject will be excluded from the PPS analysis under the following conditions

Code	Condition under which the code is used
800	Fraudulent data
900	Invalid informed consent
1030	Study vaccine not administered at all
1050	Randomization failure
1060	Randomization code was broken
1070	Subjects got vaccinated with the correct vaccine but containing a lower volume
1070	Vaccination not according to protocol (wrong site to be evaluated case-by-case, wrong route)

Code	Condition under which the code is used
1080	Vaccine temperature deviation
1090	Expired vaccine administered
2010	Protocol violation (inclusion/exclusion criteria)
2040	Administration of any medication forbidden by the protocol
2080	Subjects did not comply with vaccination schedule (missed or out of window of any study vaccination)
2090	Subjects did not comply with blood sample schedule
2100	Serological results not available (blood draw not performed, no results back from the lab)
2120	Obvious incoherence or abnormality or error in data
2130	Central/internal/external lab deviations

#### 4.2.4.2. Right censored Data

Data from a subject will be censored from visit x for the FAS and PPS analysis under the following conditions. The code \*\*\*\*.X+ will also be used to identify study withdrawal from visit x.

Code	Condition under which the code is used
1060.x+	Randomization code was broken
1070.x+	Vaccination not according to protocol

#### 4.2.4.3. Visit-specific censored Data

Data from visit x will be censored for the FAS and PPS analysis under the following conditions.

Code	Condition under which the code is used
1070.X	Subjects got vaccinated with the correct vaccine but containing a lower volume
	Vaccination not according to protocol (wrong site to be evaluated case-by-case, wrong route)
1080.X	Vaccine temperature deviation
1090.X	Expired vaccine administered
2040.X	Administration of any medication forbidden by the protocol
2080.X	Subjects did not comply with vaccination schedule (missed or out of window of any study vaccination)
2090.X	Subjects did not comply with blood sample schedule at visit x
2100.X	Serological results not available (blood draw not performed, no results back from the lab)
2120.X	Obvious incoherence or abnormality or error in data
2130.X	Central/internal/external lab deviations
2150.X	Subject did not provide any post-vaccination unsolicited safety data
2160.X	Subject did not provide any post-vaccination solicited safety data

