**4.1.4. Full Analysis Set (FAS) for Immunogenicity**

All subjects in the Exposed Set who provide immunogenicity data at either one month after their 4th vaccination or one month after their 3rd vaccination for at least 1 antigen/strain.

In case of vaccination error, subjects in the FAS sets will be analysed “as randomized” (i.e., according to the vaccine a subject was designated to receive, which may be different from the vaccine the subject actually received).

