**4.1.5. Per Protocol (PP) Set for Immunogenicity**

All subjects in the FAS Immunogenicity who:

- Correctly receive the vaccine (i.e., receive the vaccine to which the subjects are randomized and at the scheduled time points).
- Have no protocol deviations leading to exclusion in at least one timepoint of analyses for immunogenicity.
- Are not excluded due to other reasons defined prior to unblinding or analysis.

Examples for subjects excluded due to other reasons than protocol deviations are:

- Subjects who withdrew informed consent.

Examples for subjects excluded due to protocol deviations are:

- Subjects who did not receive all the study vaccines up to Dose 3 for primary 3 doses analyses or up to Dose 4 for the 4th dose analyses.
- who received a vaccine not specified or forbidden in the protocol up to Visit 4 for primary 3 doses or up to Visit 6 for the 4th dose.

- who received a medication/product leading to exclusion from a per-protocol analysis as listed in Protocol Section 6.7.2 up to Visit 4 for primary 3 doses or up to Visit 6 for the 4th dose.
- who presented a medical condition leading to exclusion from a per-protocol analysis as listed in Protocol Section 6.8 up to Visit 4 for primary 3 doses or up to Visit 6 for the 4th dose.
- who did not comply with the post Dose 3 (for primary 3 doses) or pre and post Dose 4 (for the 4th dose) blood sample schedule, i.e. 21 to 60 days post the vaccination.
- who had no immunogenicity results post Dose 3 (for primary 3 doses) or post Dose 4 (for the 4th dose).

The allowed intervals between each study visit are given in [Table 5](#). Subjects will not be eligible for inclusion in the per-protocol cohort for analysis of primary 3 doses if study visits are performed outside this interval up to visit 4, and they will not be eligible for analysis of the 4th dose if the study visit is performed outside this interval up to Visit 6.

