#### 4.2.4.4. Vaccine-specific censored Data

Data from vaccine X will be censored for the FAS and PPS analysis under the following conditions:

- a. Bexsero/Placebo
- b. Prevnar 13 / Prevnar 20
- c. Pediarix
- d. Hiberix
- e. MMR
- f. Varivax

Code	Condition under which the code is used
1070.X	Subjects got vaccinated with the correct vaccine but containing a lower volume
	Vaccination not according to protocol (wrong site to be evaluated case-by-case, wrong route)
2080.X	Subjects did not comply with vaccination schedule (missed or out of window of any study vaccination)

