## **5.3. Immunogenicity**

### **5.3.1. Analysis of immunogenicity planned in the protocol**

The primary population for the primary and secondary immunogenicity analyses will be the PPS. All primary and selected secondary immunogenicity analyses (NI assessments for other RIVs) will be repeated on the FAS. Detail on selected Tables will be given in OPS.

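### The SAP censors FAS data on most per-protocol elimination codes, contradicting its own FAS definition and weakening the FAS repeat as a check on excluding deviators

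*SAP*

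**What the plan says.** **FAS definition.** SAP 4.1.4 and protocol 9.2.4 include exposed subjects with immunogenicity data one month after dose 3 or dose 4 for at least one antigen or strain. Neither lists a protocol deviation as a reason to leave the set. Both analyse subjects with a vaccination error by randomized arm, that is, "according to the vaccine a subject was designated to receive, which may be different from the vaccine the subject actually received".

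**Censoring rules.** These sit in SAP 4.2.4, under a heading about elimination from the PPS.
- 4.2.4.1: "A subject will be excluded from the PPS analysis under the following conditions", followed by the list of codes.
- 4.2.4.2: "Data from a subject will be censored from visit x for the FAS and PPS analysis under the following conditions". The codes are 1060.x+ and 1070.x+.
- 4.2.4.3: "Data from visit x will be censored for the FAS and PPS analysis under the following conditions". The codes include 2160.X, "Subject did not provide any post-vaccination solicited safety data", and its unsolicited counterpart 2150.X.
- 4.2.4.4: "Data from vaccine X will be censored for the FAS and PPS analysis under the following conditions". The codes are 1070.X and 2080.X.

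**Role of the FAS.** SAP 5.3.1 makes the PPS primary and adds: "All primary and selected secondary immunogenicity analyses (NI assessments for other RIVs) will be repeated on the FAS".

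**Declared changes.** SAP Section 8 records a change to the PPS definition. It does not mention any censoring of the FAS.

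**The concern.** The usual reason to repeat a per-protocol immunogenicity analysis on a full analysis set is to see whether leaving out deviators affected the answer. That works only if the deviators' results are in the second set. Here the same deviation codes remove data from both sets, so the two could agree largely because they hold much the same data.

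The rules also conflict. Code 1070.x+, vaccination not according to protocol, censors a subject from that visit on, whereas 4.1.4 keeps vaccination errors as randomized. Read literally, codes 2150 and 2160 could drop a valid serology result because safety data were not provided.

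At stake is the robustness check for all 23 primary hypotheses and for the non-inferiority assessments of the other routine vaccines. The PCV20 sensitivity analyses in SAP 5.3.2.1 address a different question and do not replace it.

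**Working it through.** **1. Count the codes.**

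| Group | Codes | Number |
|---|---|---|
| PPS exclusion codes (SAP 4.2.4.1) | 800, 900, 1030, 1050, 1060, 1070, 1080, 1090, 2010, 2040, 2080, 2090, 2100, 2120, 2130 | 15 |
| Of these, also censoring the FAS (4.2.4.2 to 4.2.4.4) | 1060, 1070, 1080, 1090, 2040, 2080, 2090, 2100, 2120, 2130 | 10 |
| Of these, acting through the Exposed Set (4.2.1) | 800, 900, 1030 | 3 |
| PPS only | 1050, 2010 | 15 − 10 − 3 = 2 |
| Censoring the FAS but not PPS exclusion codes | 2150, 2160 | 2 |

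The overlap is 10/15 = 67% directly and 13/15 = 87% with the Exposed Set codes. Not all of it is a fault. Code 2100 means there is no result. Codes 2120 and 2130 can be justified when a result is invalid. The three Exposed Set codes belong there. The contested codes are the other seven: 1060 (code broken), 1070 (vaccination not per protocol), 1080 (temperature deviation), 1090 (expired vaccine), 2040 (forbidden medication), 2080 (vaccination schedule) and 2090 (blood-sample schedule).

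**2. What `.X` could mean.** Protocol 5.6.12 places study vaccination at Visits 1, 2, 3 and 5. Protocol 5.6.11.1 places blood draws at Visits 4, 5 and 6. Take a temperature deviation at Visit 2.
- If `.X` covers only the visit where the deviation occurred, no serology is removed from the FAS.
- If it covers the results that depend on that dose, the Visit 4 result or later ones go.

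On the first reading the FAS keeps some results that the PPS drops, because the PPS rules in 4.1.5 accumulate: a subject is out of the dose-4 analysis "if the study visit is performed outside this interval up to Visit 6". The text does not settle which reading applies.

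**3. Illustration of possible size.** The documents give a 40% drop-out rate (protocol 9.1) but no deviation rate, so the number of deviators and their response below are assumptions.

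The base case uses the means and SDs in protocol Tables 18 and 19 with zero correlation. For each strain, P(titer ≥ cut-off) = Φ((mean − log10 cut-off)/SD) after dose 4:
- M13520: (1.41225 − log10 8)/0.36477 gives 0.9186
- NZ98/254: (1.57978 − log10 8)/0.53796 gives 0.8958
- M14459: (1.53148 − log10 8)/0.45097 gives 0.9183
- 96217: (3.06183 − log10 16)/0.63454 gives 0.9983

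The composite is 0.9186 × 0.8958 × 0.9183 × 0.9983 = 0.754, or 362 of 480. The exact (Clopper-Pearson) lower limit of the two-sided 96.67% interval is 71.0%, against the 65% margin.

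Now add deviators who have a result. For example, 160 responding at 40% give (362 + 64)/(480 + 160) = 426/640. Lower limits:

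| Deviators added | Respond 40% | 50% | 60% | 70% |
|---|---|---|---|---|
| 80 | 66.0% | 67.5% | 69.0% | 70.5% |
| 160 | 62.4% | 65.0% | 67.6% | 70.2% |
| 240 | 59.7% | 63.1% | 66.5% | 69.9% |

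Three of the 12 cells fall below 65%, and 160 at 50% sits on the margin. If no deviator has a result, nothing changes.

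**The case against.** The strongest reply has four parts.

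- **Membership is not data.** Section 4.1.4 says who is in the FAS, and 4.2.4.2 to 4.2.4.4 say which data are used, so a subject can stay in the set with some results removed. That is formally true. But the repeat analysis runs on data, and analysing a subject as randomized means nothing once the result is gone.
- **The 1070 conflict may be narrower than it looks.** The as-randomized sentence describes receiving a different vaccine. Code 1070 in 4.2.4.1, 4.2.4.3 and 4.2.4.4 describes a lower volume, wrong site or wrong route. This is fair for those rows. The 1070.x+ row in 4.2.4.2 has no such qualifier, so it can catch the mix-ups that 4.1.4 keeps.
- **Some censoring fits the definition.** The FAS asks for data one month after a dose, so dropping an off-schedule sample, or a post-dose-4 result when dose 4 was missed, is arguable. This softens 2090 and part of 2080. It does not cover doses given out of window, forbidden medication, temperature deviation, expired vaccine or a broken code.
- **Little may follow.** Read literally, visit-level censoring at a vaccination visit removes no Visit 4 or Visit 6 serology. No deviation rate is given, and the cells below 65% need at least 160 deviators responding at 40%, or 240 at 40% or 50%, against 75.4% in the PPS. Protocol 9.8 also requires departures from the planned statistics to be justified in the report. All of this stands, and it limits the severity. It does not make the two sets of rules consistent.

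**Conclusion.** The concern holds. As written, SAP 4.2.4.2 to 4.2.4.4 contradict the FAS definition in SAP 4.1.4 and protocol 9.2.4, and Section 8 does not declare the departure. By code the overlap is 13 of 15. After setting aside the codes that properly remove absent or invalid data, seven deviation codes are wrongly shared, and 2150 and 2160 do not belong in an immunogenicity list.

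The loss of information cannot be quantified from the documents, because it depends on the undefined `.X` and on an unstated deviation rate. The illustration assumes independent strains, the protocol's planning means and SDs, and deviators who have results. Under those assumptions an uncensored FAS would miss the 65% margin only with many deviators who respond far less often than the PPS.

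No primary conclusion depends on the FAS, so this should be fixed but does not threaten the trial's success criteria. The contradiction and the code counts are certain from the text. The practical impact is not.

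**What to change.** - In SAP 4.2.4.2, 4.2.4.3 and 4.2.4.4, apply the censoring to the PPS only.
- For the FAS, list the exclusions that remain: no result (2100), erroneous or invalid data (2120, and 2130 where the result is analytically invalid), and the Exposed Set codes 800, 900 and 1030.
- Remove 2150 and 2160 from the immunogenicity list. They are already handled in 4.2.2 and 4.2.3.
- State whether `.X` means the visit where the deviation occurred or the serology timepoints that depend on it.
- If any other FAS censoring is intended, declare it with its reason in Section 8.

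The cost is three wording edits, one definition and a small change to the FAS flag programming. No new data are needed. FAS results may come out slightly less favourable than PPS results.

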#### 4.2.4.4. Vaccine-specific censored Data

Data from vaccine X will be censored for the FAS and PPS analysis under the following conditions:

- a. Bexsero/Placebo
- b. Prevnar 13 / Prevnar 20
- c. Pediarix
- d. Hiberix
- e. MMR
- f. Varivax

Code	Condition under which the code is used
1070.X	Subjects got vaccinated with the correct vaccine but containing a lower volume
	Vaccination not according to protocol (wrong site to be evaluated case-by-case, wrong route)
2080.X	Subjects did not comply with vaccination schedule (missed or out of window of any study vaccination)

#### **4.3. Important protocol deviation not leading to elimination from per-protocol analysis set**

Not applicable

### **5. STATISTICAL ANALYSES**

Note that standard data derivation rule and statistical methods are described in [Annex 1](#) and will not be repeated below.

Subjects who received PCV20 at Visit 5 are analysed together with the subjects who received PCV13. Sensitivity analyses will be performed on immunogenicity analyses excluding subjects who received PCV20 as described in Section [5.3.2.1](#).

#### **5.1. Demography**

##### **5.1.1. Analysis of demographics/baseline characteristics planned in the protocol**

Descriptive statistics (mean, standard deviation, median, minimum, and maximum) for age (at enrolment, for the Enrolled Set and at first vaccination, for the Exposed Set) and for height and weight at enrolment will be calculated overall and by vaccine group.

Distributions of subjects by sex, race, ethnic origin, geographic region and age group (6-8 weeks or  $\geq 8$  weeks) will be summarized overall and by vaccine group.

### **5.1.2. Additional considerations**

The number of subjects with suspected, probable or confirmed COVID-19 infection will be summarized by vaccine group and across diagnoses. This summary will be provided for the Exposed Set.

The number of exposed participants who discontinued the study will be tabulated by vaccine group with the reason for discontinuation. The summary table will be produced by relationship to COVID-19.

A summary table of important protocol deviations by relationship (related/not related) to COVID-19 will be provided.

## **5.2. Exposure**

### **5.2.1. Analysis of exposure planned in the protocol**

The frequencies and percentages of subjects with vaccinations will be summarized by vaccine group, vaccination number and overall. Data will be tabulated for the Exposed Set.

### **5.2.2. Additional considerations**

Not applicable.

## **5.3. Immunogenicity**

### **5.3.1. Analysis of immunogenicity planned in the protocol**

The primary population for the primary and secondary immunogenicity analyses will be the PPS. All primary and selected secondary immunogenicity analyses (NI assessments for other RIVs) will be repeated on the FAS. Detail on selected Tables will be given in OPS.

#### **5.3.1.1. Within groups assessment**

For each study group the following endpoints will be assessed related to MenB strains and PCV13 strains:

- the percentage of subjects with hSBA titers  $\geq$  LLOQ for each of the M14459, 96217, NZ98/254 and M13520 test strains and for all strains combined, at each timepoint that a blood sample result will be available
- the percentage of subjects with hSBA titers  $\geq 5$ ,  $\geq 8$  and  $\geq 16$  for each of the M14459, 96217, NZ98/254 and M13520 test strains, at each timepoint that a blood sample result will be available
- the percentages of subjects with hSBA titers  $\geq 8$  for each of the test strains (M14459, NZ98/254 and M13520),  $\geq 16$  for test strain 96217, and for all strains combined (composite endpoint) at one month after the 4th vaccination

- the percentage of subjects with 4-fold increase at post-4th (from pre-4th vaccination) for each of the M14459, 96217, NZ98/254 and M13520 test strains
- GMCs/GMTs and within group GMRs (for post-4th versus pre-4th titers) will be tabulated for antibodies for each antigen, at each timepoint that a blood sample result will be available
- Percentage of subjects with serum pneumococcal anti-capsular polysaccharide IgG  $\geq 0.35$   $\mu$ g/mL at one month after the 3rd and 4th vaccination in Group MenB+PCV and Group Placebo+PCV.

The CIs will be calculated as 2-sided 95% for exploratory objectives and will be calculated at given alpha at the testing step for the primary objectives that are associated with statistical hypothesis testing.

Endpoints associated with the other RIV will be assessed within-group as specified in Section 3. The 2-sided 95% CIs will be calculated.

#### **5.3.1.2. Between groups assessment**

For PCV antigens, at blood sampling timepoint one month post 3rd and one month post 4th vaccination and for each antibody for which results are available, for Diphtheria, Tetanus, Pertussis and Hepatitis B antigens, at blood sampling timepoint one month post 3rd vaccination, for VV and MMR, at blood sampling timepoint one month post 4th vaccination and for each antibody for which results are available:

- The CIs of the between-group GMC ratios (i.e. study group minus control group) will be computed using an analysis of variance (ANOVA) model on the logarithm10 transformation of the concentrations.

For Diphtheria, Tetanus, Hib, Polio and Hepatitis B antigens, at blood sampling timepoint one month after the 3rd vaccination, for VV and MMR, at blood sampling timepoint one month after the 4th vaccination and for each antibody for which results are available:

- The CIs of the between-group percentage differences (i.e. study group minus control group) will be computed.

#### **5.3.1.3. Analysis of Primary Immunogenicity Objectives**

##### *Statistical Hypotheses*

In total 23 hypotheses will be tested for the primary objectives. A stepwise statistical approach will be used for the 23 statistical tests. The hypotheses will be grouped into three families, based on the different immunogenicity objectives:

Family 1: 13 statistical hypotheses related to non-inferiority of PCV13 with rMenB+OMV NZ as measured by the GMCs of the 13 PCV13 antigens, after the 3rd vaccination.

Family 2: 5 statistical hypotheses related to sufficiency objective on percentage of subjects with hSBA titers  $\geq 8$  (for strains M14459, NZ98/254, M13520) and  $\geq 16$  (for strain 96217) at one month post 4th dose, and the composite endpoint

Family 3: 5 statistical hypotheses related to sufficiency objective on percentage of subjects with hSBA titers  $\geq$  LLOQ at one month post 3rd dose for each of the four strains M14459, 96217, NZ98/254, and M13520, and the composite endpoint

Each family of hypotheses is linked to an objective, as follows:

- Family 1 is related to the “immunological non-inferiority of rMenB+OMV NZ + PCV13 compared to PCV13 after the 3rd vaccination” objective.
- Families 2 and 3 are related to the “*sufficiency of the immune response to rMenB+OMV NZ*” objective at one month post 4th dose and one month post 3rd dose, respectively.

The statistical hypotheses for each and all families are formulated as below:

